1. SUMMARY

Cardiovascular disease (CVD) is the leading cause of death worldwide. The most important cardiovascular risk factors are modifiable, and it has been shown that an adequate diet is essential for the prevention of CVD due to its effect on blood pressure, lipids, obesity, inflammation and endothelial function. Among the main dietary macronutrients, saturated fatty acids (SFA) are of interest for their effects on the elevation of low-density lipoprotein cholesterol (LDL-C) and total cholesterol, which are associated with increased cardiovascular risk due to endothelial dysfunction and atherosclerosis. However, recent research suggests that not all SFA exerts the same effects and that certain foods such as red and processed meats contain a more unfavourable SFA profile, which can have important repercussions in relation to cardiovascular risk. The CADIMED study is an eight-week randomized, controlled intervention study comparing the effect of an intervention that promotes the reduction of red and processed meat intake in a sample of 156 adult subjects (>18 years) and dyslipidaemia. **Objectives:** 1) To develop a dietary intervention that promotes the reduction of consumption of SFA from red and processed meats in patients with elevated LDL-C; 2) To determine the efficacy of this dietary intervention aimed at eliminating red and processed meat, in the context of a Mediterranean dietary pattern, on LDL-C and palmitic acid after eight weeks of intervention (main objective); 3) To determine the metabolic alterations parallel to the modifications in the intake of SFA from red and processed meat, using a complete lipid and metabolomic profile and other markers of cardiovascular risk (biomarkers of inflammation, endothelial damage, insulin resistance and diabetes; changes in blood pressure; anthropometry and C-reactive protein); 4) To assess the effect of the intervention on dietary intake of various nutrients and other lifestyle factors; 5) To evaluate the effect of the intervention on metabolites derived from the gut microbiota; 6) Establish a working panel with patient and public participation (PPP) as well as health professionals, to improve research management and dissemination of project results.

Keywords: cardiovascular disease, Mediterranean diet, saturated fats, LDL cholesterol, red meat, palmitic acid.

2. BACKGROUND

Worldwide, cardiovascular disease (CVD) is the leading cause of mortality; the World Health Organization estimates that, in 2019, 32% of deaths worldwide were caused by CVD, mainly acute myocardial infarction.¹ The most important cardiovascular risk factors are modifiable and are associated with poor diet, lack of physical activity, tobacco and alcohol use. Among them, it has been shown that an adequate diet is essential for the prevention of CVD given its effects on blood pressure, lipids, obesity, inflammation and endothelial function.² Of the dietary macronutrients, saturated fatty acids (SFA) are of great interest due to their effects on the elevation of low-density lipoprotein cholesterol (LDL-C) and total cholesterol, which are associated with increased cardiovascular risk due to endothelial dysfunction and atherosclerosis.³ Because of this, recommendations from different organizations and institutions, such as the *American Heart Association* and the *European Society of Cardiology*, indicate that AGS should represent less than 10% of total energy intake,⁴ preferably between 5% and 6%, to prevent CVD.⁵ A meta-analysis of clinical trials by the Cochrane group has shown that reducing SFA consumption significantly decreases LDL-C and up to 17% cardiovascular events.⁶

However, current clinical practice guidelines on the prevention and treatment of CVD propose a healthy diet generally low in SFA but without offering detailed or specific advice for effective intervention.^{4,7} This is important as different food sources of SFA could pose different health risks.⁸ Foods contain complex mixtures of SFA and evidence suggests that some of them, such as lauric, myristic, and palmitic acid, may pose different risks.^{9,10} Red meat contains a large proportion of palmitic acid [long-chain SFA (16:0)] and, although the current evidence is inconsistent and based mostly on observational studies, an increased risk of CVD associated with a higher intake of red and processed meat, compared to plant protein sources, has been documented, probably mediated by changes in the lipid profile, inflammatory or insulin resistance.^{11,12} However, other SFA-rich foods, such as milk and cheese, contain large proportions of shorter-chain [lauric (12:0) and myristic (14:0)] fatty acids and have not been shown to be associated with CVD.¹³ It has been suggested that dairy products have other elements such as calcium, which could counteract the unfavourable physiological effects of SFA.¹⁴

The principal investigator of this project has recently led a preliminary intervention study for the reduction of dietary saturated fat in a population with cardiovascular risk.¹⁹ The final results found a non-significant decrease in SFA intake and beneficial changes in blood lipid profile were observed among those participants who reduced their consumption of red and processed meats the most, compared to those who reduced other sources of SFA such as dairy.¹⁹ Ultimately, the scant current evidence suggests that different sources of SFA and individual proportions of SFA in red and processed meat may influence cardiovascular profile differently, although robust intervention studies are still needed to confirm this. Likewise, changes in the fatty acid and blood lipid profile resulting from a dietary approach based on a Mediterranean diet pattern along with the elimination of red and processed meat consumption are largely unknown. Therefore, it is important to investigate how these dietary modifications affect cardiovascular risk factors in the context of a Mediterranean diet in which

the consumption of unsaturated fats from olive oil or nuts is positively associated with less CVD.¹⁵

On the other hand, it is worth mentioning that despite recent efforts in public health, the reduction of SFA consumption through education or information programs in the population has not been sufficient. Previous research establishes that it is possible to reduce the intake of products rich in SFA by providing foods that replace them, and/or through intensive and adapted dietary advice, with the participation of specialized personnel and behavioural support.¹⁵⁻¹⁸ However, there is little evidence on the effectiveness of other less intensive and low-cost interventions that can reach a larger number of people and have a significant effect on the population. Simple, food-specific dietary guidance (e.g., red meat) related to cardiovascular risk may have greater potential to be easily disseminated and adopted by a large number of primary care patients who need help to improve the quality of their diets and thus decrease their cardiovascular risk.

Based on what has been described, the CADIMED study aims to develop and test the efficacy of a dietary intervention to reduce the consumption of SFA from red and processed meat and to evaluate the effects on various biomarkers of cardiovascular risk in adults with dyslipidaemia. The determination of the lipid profile, metabolomic profile and the composition of the intestinal microbiota will allow a better understanding of the questions raised and will help to establish simple dietary guidelines based on a better approach for the treatment of dyslipidaemia and the prevention of CVD, relevant to the third Sustainable Development Goal (SDG) of the United Nations. The low cost and scalability of the intervention can help the Spanish health system, specifically primary care, particularly by helping the management of patients at risk of CVD, reducing the affected population and healthcare costs. In addition, the decrease in the consumption of red and processed meat also implies effects on global warming and environmental sustainability, contributing to achieving the 12th SDG.

3. HYPOTHESIS

A dietary intervention based on the exclusion of red and processed meat within a Mediterranean dietary pattern will have a better effect on lipid profile and cardiovascular risk markers compared to the usual recommendation to follow a healthier lifestyle.

4. OBJECTIVES

4.1. General objective:

To develop and determine the efficacy of a dietary intervention that promotes the elimination of SFA consumption from red and processed meats and to evaluate its impact on lipid and cardiovascular risk markers in patients with dyslipidaemia.

4.2. Specific objectives:

- a. To develop the necessary elements for the application of a dietary intervention that promotes the reduction of the consumption of SFA from red and processed meats in patients with dyslipidaemia
- b. To test the efficacy of a dietary approach aimed at avoiding red and processed meat, in the context of a Mediterranean dietary pattern, on LDL-C and palmitic acid (main results) after eight weeks of intervention, compared to the usual approach of healthier lifestyle recommendations.
- c. To determine the metabolic alterations parallel to the changes in SFA intake, from red and processed meat, by means of a complete lipid and metabolomic profile, as well as the determination of other intermediate markers of CVD.
- d. To assess the effect of the intervention on dietary intake and other lifestyle factors.
- e. To evaluate the effect of the intervention on the composition of the gut microbiota and its derived plasma metabolites that could be influenced given the expected metabolic benefits;
- f. Establish a working panel with patient and public participation (PPP) as well as health professionals, to improve research management and dissemination of project results.

5. METHODOLOGY

5.1. Experimental design

The CADIMED study is a randomized, controlled (two parallel arms) dietary intervention study, where the effect of an eight-week behavioural intervention consisting of a Mediterranean dietary pattern with elimination of red and processed meat will be evaluated, compared to the general advice for decreasing SFA intake in patients with elevated LDL-C.

To this end, 156 patients ≥ 18 years of age with dyslipidaemia and who express their desire to improve their diet and reduce the risk of CVD will be recruited. The study will be registered in ClinicalTrials.gov and a Good Clinical Practice and Trial Quality Assurance strategy will be established (see section 11 for other ethical and legal considerations).

5.2. Study population

Inclusion criteria:

- 1) Signed informed consent;
- 2) Age ≥ 18 years to ≤ 75 years;
- 3) Indicated to start lifestyle intervention based on recent values (e.g., last 3-6 months) of LDL-C ≥ 116 mg/dL and < 190 mg/dL; as long as pharmacological intervention has not been advised and started (*ESC/EAS Guideline, Rev Esp Cardiol. 2020*);
- 4) Device access (e.g. *smartphone, tablet*) with internet and digital skills for the use of the mobile application;
- 5) Motivation and willingness to be assigned to any of the groups to improve their diet, as well as commitment to carry out the assigned protocol.

Exclusion criteria:

- 1) Patients with familial hypercholesterolemia and/or on treatment with lipid-lowering drugs (including statins, ezetimibe, PCSK9 inhibitors, fibrates, bile acid chelators, Omega 3 fatty acids, nicotinic acid/Vit B3), dietary supplements or functional foods for the treatment of dyslipidaemia (plant sterols, monacolin, red rice yeast, fibre supplements 3-10g (plantago), policosanol, berberine and soy protein/lecithin) in the last 3 months;
- 2) Cardiovascular risk that makes the use of drugs necessary, for example, in patients with recent and/or established CVD; type 1 and 2 diabetes;
- 3) Uncompensated thyroid function disorders; relevant comorbidities (including liver failure and cholestasis, chronic kidney disease, Cushing's syndrome, nephrotic syndrome, obesity grade III – BMI > 40 kg/m²); cancer; psychiatric disorders and/or that in the opinion of the researcher makes it difficult to comply with or follow up on the study;
- 4) Excessive alcohol consumption: > 40 g/d (4 UBEs/day) in men and $> 20-25$ g/d (2-2.5 UBEs/day) in women (*Ministry of Health, July 2020*)

- 4) Pregnancy, lactation, perimenopause (amenorrhea <1 year), and women who change, start, or end hormonal contraceptive treatment during the study;
- 5) Participation in other research or dietary pattern (e.g. vegetarian and vegan) that could interfere with the demands of the study;
- 6) Failure to provide informed consent or failure to complete the initial assessment.

5.3. Procedure and data collection

All data collected from patients will be stored in a password-protected database and encrypted/pseudonymized with a unique code for each patient. The code will consist of two letters (initials of the health centre where the patients come from) and three numbers that will be assigned in ascending order. Only the research team and the health authorities, who have a duty of confidentiality, will have access to all the data collected for the study. Only information that cannot be identified may be transmitted to third parties.

- 1) Patient recruitment and pre-selection: Initial recruitment will be done through health professionals in primary or secondary care practices, who will help distribute information and participation in the study. Interested persons will contact the research team via telephone or email to confirm that they meet the inclusion requirements through a brief initial pre-selection questionnaire (Annex 1 – Pre-selection Questionnaire). Volunteers who meet the inclusion requirements will be personally scheduled for an initial visit with the research team and the clinical team at the Virgen de las Nieves hospital (Granada).
- 2) Informed Consent: During the first initial visit with the research team, study information will be given to patients (Patient Information Sheet and Informed Consent) and the informed consent will be read and signed. The opportunity to resolve issues related to the study and participation will be offered and those who complete the informed consent will become part of the study.
- 3) Questionnaires and measures: The research team will administer during the initial visit a general questionnaire to obtain the patient's demographic characteristics, including age, sex, education, socioeconomic class, alcohol intake, physical activity, diet and smoking (Annex 2 – Data collection notebook). The clinical team (nurse from the Virgen de las Nieves Hospital with links to the project) will be responsible for taking clinical data related to the medical history and/or use of relevant medications. Height, weight and blood pressure will then be measured at the beginning and at the follow-up in a standardized manner.

In addition, help will be offered to access and use a mobile application (designed especially for the study) to start collecting data on diet. The app will include each patient's unique code and a built-in diet questionnaire that will need to be completed at least twice a week (ideally every day), during the first and last week of the intervention to obtain valid measures of usual intake. In addition, a questionnaire on the frequency of food consumption during the previous 4 weeks will be completed to assess the eating pattern.

4) Blood samples: the nurse in charge of the project will take blood samples during the 1st initial visit and at the end of the follow-up of each patient, with an overnight fast of 8 hours. The samples will be processed in the laboratory of the Virgen de las Nieves Hospital for subsequent analysis in the same hospital; in addition to the transfer/storage of the remaining samples in our laboratory of the Institute of Nutrition and Food Technology (INYTA) (details on page 11-12).

5) Stool samples: stool samples will be taken at the beginning and end of follow-up for which patients will be provided with the necessary material and instructions for collection (e.g. taking antibiotics) and storage of the samples. The samples will be delivered to the research team during the 2nd initial visit for processing and storage in our laboratory at the Institute of Nutrition and Food Technology (INYTA).

6) Randomization and assignment of the intervention group. During the 2nd initial visit, and once it has been confirmed that patients meet all the inclusion requirements, the intervention group will be randomly assigned and the corresponding explanation to the patient will be carried out.

Table 1. Data collection at CADIMED study visits

	Evaluation Preview	1st visit initial	2nd visit initial	Visit End
a. Pre-selection questionnaire (via telephone)	x			
b. Signed consent		x		
c. General questionnaire (demographics, lifestyle)		x		x
d. Anthropometric measurements, blood pressure, clinical data		x		x
e. Physical activity questionnaires, 24-hour food and diet patterns		x	x	x
f. Blood sample collection		x		x
g. Stool sample collection			x	x
h. Randomization and Intervention Allocation			x	

5.4. Intervention

Participants will be randomly assigned, in a 1:1 ratio, to one of two groups:

Intervention group: Mediterranean diet without red and/or processed meat

They will receive motivation and behavioural support through the use of the mobile application, which will provide them with reminders to self-monitor their changes in eating; while the rest of the clinical care will be usual. After randomization of the patients, the research team will give them more information about the use of the mobile app, with specific

indications to avoid red and processed meat in the context of a healthy Mediterranean dietary pattern, taking into account the key elements proposed in the dietary guidelines for CVD prevention. The app will provide details of Mediterranean diet recommendations, as well as recipes, tips and alternatives to replace meat when cooking at home or eating out. Participants will record their daily diet through the mobile application, during the first and last week of the intervention. The rest of the clinical care will be usual.

Control group: Mediterranean Diet

Similarly, the control group will be helped to download and use the mobile application, although they will only have access to a restricted version of it, by which they will receive brief and general information to maintain a healthy lifestyle following the general guidelines on the Mediterranean diet (without specific recommendations to reduce red and processed meat). Participants will also record their daily diet through the app, during the first and last week of the intervention. The rest of the clinical care will be usual.

5.5. Randomization

Randomization will be computer-generated, with sex, age, obesity, and diet (fiber intake) as stratification variables using random blocks of size 2 and 4. The computer program will reveal the group assigned at the same time to the researcher, without the option of viewing the groups that will be assigned to future patients.

It will not be possible to blind patients to the intervention group due to the nature of the intervention; however, the primary outcomes of efficacy measures will be objectively measured (blood lipids) and are not subject to interpretation by investigators. To the extent possible, the study team performing all measurements will remain blind to group assignment during the study.

5.6. Definition of variables: main and secondary results

With the determinations and measurements derived from the CADIMED study, it is proposed to investigate the following results (comparing the intervention group and the control group):

- 1) Main results: changes in LDL-C and fatty acid profile in erythrocytes after 8 weeks of intervention
- 2) Secondary outcomes:
 - a. Changes in other metabolites derived from lipid and metabolomic profile analysis, including circulating fatty acids, HDL-C, total cholesterol, triglycerides, and endogenous and exogenous metabolites related to cardiovascular risk and meat consumption (e.g., TMAO, etc.);
 - b. Changes in other related markers of cardiovascular risk, including biomarkers of inflammation and endothelial damage, insulin resistance, and diabetes (glucose, insulin, HbA1c, C-reactive protein, IL6, TNF-alpha), blood pressure, weight, and body and waist mass index;

- c. Changes in the gut microbiota and derived metabolites
- d. Changes in dietary intake (measured by 24-h recall): SFA intake, total energy intake, total fat, sugar, fiber, salt, general dietary patterns, red and processed meat consumption.
- e. Changes in other lifestyle-related factors: collected through physical activity, smoking, and alcohol questionnaires

3) **Evaluation of the process**: analyses of both quantitative and qualitative measures will be included to understand whether the intervention has worked and through which processes. These measures include: the rate of recruitment of volunteers and the rate of patients completing the study; acceptance of the intervention through questionnaires at the end of follow-up; the use of the mobile application to carry out changes in the diet as well as the self-monitoring of intake; measures that evidence the contamination of the control group; changes in patients' ability and knowledge about diet, SFA, and cardiovascular disease.

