5.7. Data analysis

Sample size

A recent randomized, controlled, peer-to-population trial testing similar dietary approaches to reduce SFA intake showed a long-term change in LDL-C of approximately 15 mg/dL (SD26).¹⁹ If 78 participants are recruited in each group ($n = 156$), it is expected to detect a minimum difference of 15 mg/dl between the intervention group and the control, with a power or detection capacity of 90%, an error $\alpha = 0.05$ and a dropout rate of 20% using intention-to-treat analysis, so the final sample size includes an additional 20% of participants to mitigate dropouts.

Statistical analysis of primary and secondary outcomes

Baseline characteristics will be summarized in descriptive statistics in each study group, statistical analysis will be performed with STATA IC 16.0 software (College Station, TX: StataCorp LLC 2019). Descriptive statistics will be presented with standard deviation (SD) and 95% confidence intervals. Continuous variables will be presented as mean and standard deviation unless the use of the median and interquartile range is necessary; Categorical variables will be expressed as frequencies and percentages.

Efficacy results will be analysed by intent to treat, i.e., all participants will be assessed according to the group to which they are randomly assigned, regardless of their adherence. The analysis of effectiveness measures will use data from all participants for whom a baseline and monitoring measure exists. A linear regression model will be used to calculate the difference in measures with 95% confidence intervals, with adjustment of the initial values of the dependent variable and the place of recruitment. Before the analysis, the assumptions of linear regression, specifically homoscedasticity and the normality of the residual distribution, will be explored. Where these assumptions are not met, appropriate non-parametric analyses shall be used. The sensitivity of the results to confounders due to

differences in baseline characteristics will also be examined. A second sensitivity analysis will use the techniques of "baseline observation carried forwards" (using the initial measure of the variable) and "multiple imputation" (using information about the assigned group and the characteristics of the participants) to impute missing values in the variables of the main outcome. An exploratory analysis of subgroups of results will be carried out according to sociodemographic characteristics.

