5.8. Determination of metabolomic profiles and gut microbiota

This project will employ a metabolic and metagenomic profiling approach (gut microbiota) using state-of-the-art analytical technologies to provide a deeper understanding of metabolic responses to dietary intervention (reduction of red/processed meat intake) in the context of a Mediterranean dietary pattern. Therefore, lipid profiling and a complete metabolomic and metagenomic analysis will be performed to investigate specific changes caused by the intervention compared to the control. The determinations will be made at the hospital (general biochemistry) as well as at the Institute of Nutrition and Food Technology (INYTA). Once the main determinations explained below have been carried out and with prior consent, the surplus samples with their corresponding code will be stored at -80°C in the Biobank of the Public Health System of Andalusia (BBSSPA), for future analyses related to the project, including aliquots with leukocytes for DNA extraction and erythrocytes for studies of antioxidant defense enzymes.

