5.8.1. Lipid metabolism, endothelial function and inflammatory markers

Fasting venipuncture blood samples will be obtained at the beginning and end of follow-up: two 10 mL tubes of K2E EDTA, and two 10 mL tubes of serum separator gel. First, part of the sample will be processed in the hospital according to its own established protocols to obtain blood biochemistries for the blood lipid fractions: total cholesterol, LDL-C (primary outcome), HDL-C, non-HDLC, triglycerides, glucose, insulin, HbA1c and CRP.

The rest of the samples will be processed at INYTA to obtain plasma and stored (-80 °C) until they are processed for analysis. The new LC-MS will be used to determine a specific plasma fatty acid profile, including palmitic acid (primary outcome), among others. Other plasma biomarkers of endothelial function, such as ICAM-1, VCAM-1, ELAM-1, and MPO, will be determined using Luminex®'s xMAP technology and MULTIPLEX kits; as well as endothelin-1 and angiotensin II using ELISA kits. Inflammatory biomarkers in plasma will also be determined with Luminex® xMAP and HSTCMAG-28SK kits, including IL-6, IL-8/CXCL8, IL-10, IL-23, TNF- α , IFN- γ . ELISA kits will be used to quantify lipopolysaccharides (LPS) and LPS-binding lipoprotein (LBP).

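### The second primary outcome has two conflicting definitions: an erythrocyte fatty acid profile in section 5.6 and plasma palmitic acid in section 5.8.1

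*Protocol*

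**What the plan says.** The protocol describes its second main outcome in four places.

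- **Section 5.6**, which defines the outcomes: "Main results: changes in LDL-C and fatty acid profile in erythrocytes after 8 weeks of intervention". Palmitic acid is not named. The first item under secondary outcomes reads "Changes in other metabolites derived from lipid and metabolomic profile analysis, including circulating fatty acids".
- **Section 5.8.1**, on laboratory methods: "The new LC-MS will be used to determine a specific plasma fatty acid profile, including palmitic acid (primary outcome), among others".
- **Section 4.2, objective b**: "on LDL-C and palmitic acid (main results) after eight weeks of intervention".
- **Section 1, summary**: "on LDL-C and palmitic acid after eight weeks of intervention (main objective".

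On sample handling, section 5.8.1 states "The rest of the samples will be processed at INYTA to obtain plasma and stored". In the laboratory sections erythrocytes appear once, in section 5.8, among surplus aliquots for the biobank: "erythrocytes for studies of antioxidant defense enzymes".

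**The concern.** A primary outcome has to be one identifiable variable before the data exist. Here the section that defines outcomes and the section that describes the assays each state a different one. They differ in compartment (red cells or plasma) and in dimension (a set of fatty acids or a single one). The linear regression in section 5.7 takes one dependent variable at a time, so a profile yields as many treatment effects as it has members, and section 5.6 names no member or summary as the one that counts.

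The stake is the credibility of the second main result. With both definitions in force, a report based on erythrocyte palmitic acid, plasma palmitic acid, or some other erythrocyte fatty acid could each cite the protocol as its pre-specification. A reader could not tell which was intended.

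**Working it through.** **1. The definitions side by side**

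| Place | Variable | Matrix | Status |
|---|---|---|---|
| Summary | palmitic acid | not stated | main |
| 4.2b | palmitic acid | not stated | main |
| 5.6, main results | fatty acid profile, no member named | erythrocytes | main |
| 5.6, secondary (a) | circulating fatty acids | circulation | secondary |
| 5.8.1 | palmitic acid within a profile | plasma | primary |

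The third and fifth rows cannot both define the second primary outcome. The first two rows contradict neither, but they do not settle the matrix. An erythrocyte primary with circulating fatty acids as secondary would be coherent within 5.6 alone. The clash arises because 5.8.1 calls the plasma measure primary.

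**2. Which version has a described measurement?** Only plasma. Section 5.8.1 gives LC-MS on plasma, and the budget in section 9 funds plasma lipid profiles. No erythrocyte fatty acid assay is described anywhere. Parts C and D of the data collection notebook (Annex 2) have a field for LDL-C but none for any fatty acid.

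**3. Is one definition superseded?** No. The change log lists three changes (nursing team, block sizes, sensitivity analyses). None concerns outcomes, so both definitions are current.

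**4. Does the sample size point to one version?** Section 5.7 gives a difference of 15 mg/dL, SD 26, α = 0.05 (taken as two-sided), power 90% and 20% dropout.

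- Normal approximation: n per arm = 2 × (1.960 + 1.282)² × 26² / 15² = 63.1, so 64. Inflation gives 64 × 1.2 = 76.8, so 77 (154 in total), or 64 / 0.8 = 80 (160 in total).
- Two-sample t-test: 64.1, so 65 per arm; 65 × 1.2 = 78 per arm, 156 in total, which is the stated figure.

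The stated size therefore reproduces, from LDL-C alone: "it is expected to detect a minimum difference of 15 mg/dl between the intervention group and the control". No effect size or SD is given for any version of the fatty acid outcome. The calculation does not show which version was meant, and the power for that outcome cannot be computed.

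**5. Illustration of the freedom left open.** The protocol does not say how many fatty acids the profile holds, so k is an assumption. With each test at 0.05 and no true effect, independent tests give 1 − 0.95^k:

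- k = 2 (palmitic acid in either matrix): 1 − 0.95² = 9.75%
- k = 10: 1 − 0.95¹⁰ = 40.1%
- k = 20: 1 − 0.95²⁰ = 64.2%

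Fatty acids measured in the same participants will be correlated. For equal correlation ρ between the test statistics, with z = 1.96, the chance is 1 − ∫ [Φ((z − √ρ·x)/√(1−ρ)) − Φ((−z − √ρ·x)/√(1−ρ))]^k φ(x) dx:

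| ρ (assumed) | k = 10 | k = 20 |
|---|---|---|
| 0 | 40% | 64% |
| 0.5 | 29% | 42% |
| 0.7 | 21% | 29% |

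**The case against.** **LDL-C is sound.** It is a main outcome wherever outcomes are named, it carries the sample size, and its analysis is stated (linear regression adjusted for baseline and place of recruitment). This stands: only the second primary outcome is unsettled.

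**Palmitic acid is named in three of the four places**, so the wording in 5.6 could be treated as a slip. That supports palmitic acid as the intended variable. It does not settle the matrix, because two of those three places state none and the third conflicts with the section whose purpose is to define outcomes.

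**The secondary item covers other metabolites**, and so could mean the circulating fatty acids left over once palmitic acid is taken out. That reading works only if plasma palmitic acid is primary, which 5.6 does not say. The double listing is a consequence of the main conflict, not a second error.

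**Red cells are available.** EDTA blood is drawn and erythrocyte aliquots are stored, so an erythrocyte assay remains possible. The supportable statement is therefore that no such assay is described, not that it could never be done.

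**Independence overstates the error rates.** This is correct, and step 5 gives the range. The finding does not depend on these rates.

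**The SAP may resolve it.** A multiplicity rule for two main results may well sit there, and its absence is not counted here. The contradiction is different: an SAP that chose one definition would still disagree with a section of the protocol.

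**Conclusion.** The concern holds. The protocol makes two incompatible statements about its second primary outcome, both in current text, and the version in the outcome-definition section has no described assay. This must be fixed before the fatty acid assays are run. LDL-C, its analysis and the total of 156 are unaffected.

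The contradiction rests on the text alone. The size of the consequence is illustrative: testing a profile member by member would carry a 21% to 40% chance of at least one false positive for 10 fatty acids and 29% to 64% for 20, over correlations from 0.7 down to 0. The numbers of acids and the correlations are assumptions.

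**What to change.** Name one second primary variable: change in palmitic acid (16:0) from baseline to week 8, in one stated matrix, by one stated assay and in one stated unit. Use identical wording in the summary, objective 4.2b, section 5.6 and section 5.8.1. Then either:

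- make it plasma palmitic acid, the only version with a described assay, and move the rest of the fatty acid profile to secondary; or
- keep the erythrocyte matrix, add the erythrocyte assay to section 5.8.1, and remove the primary label from the plasma measure.

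List each fatty acid and matrix once, as primary or as secondary.

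The cost is a wording amendment in four places and no extra participants. The plasma option needs no extra assay; the erythrocyte option adds one. Table 2 places lipid profiling in months 21 to 33, so the amendment should be dated before those assays begin.
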